To examine differences in dose reductions, dose delays and early stoppage for chemotherapy and the total combined number of moderate and severe chemotherapy-associated toxicities between intervention group and waitlist controls.

2. Secondary Objectives:

- a. To examine specific inflammatory markers (e.g. CRP, IL-6, TNF- α receptor II [TNF-RII]) in relation to baseline MM and fat mass (FM) and examine differences in changes in inflammatory markers between intervention group and waitlist controls. Inflammatory markers and body composition will be measured pre and post intervention.
- b. To examine the impact of RT induced body composition changes on the pharmacokinetics (PK) of 5-FU and oxaliplatin between baseline and 4 months of RT.

3. d3 Creatine Objectives

- a. To test whether resistance training during chemotherapy (v. control) increases d3 creatine muscle mass at 6 months.

- b. To evaluate the association of d3 creatine muscle mass with changes in functional status and strength during chemotherapy.
- c. To evaluate the association of d3 creatine muscle mass with chemotherapy toxicity and relative dose intensity.
- d. To evaluate the association of d3 creatine muscle mass with cancer-related biomarkers, including inflammation, CEA levels and cardiometabolic risk factors.

BACKGROUND

1.1 Colon cancer epidemiology and prognosis by stage:

Colorectal cancer is the 4th most common in the United States, with an estimated 134,490 individuals being diagnosed in 2016, 71% located in the colon (versus rectum)². Unfortunately, more than 49,190 individuals die from the disease annually, making colorectal cancer the second leading cause of cancer death in the United States. Surgery is the primary modality of management for colon cancer, and a ‘curative intent’ resection occurs in 80–85% of patients with non-metastatic disease (stages I-III). The benefit of adjuvant therapy has been consistently shown in multiple clinical trials, although the 5-year disease free survival for stage III disease is only 70%³.

1.2 Adjuvant chemotherapy and dosing:

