2. OBJECTIVE

2.1 Primary Objective:

To examine differences in dose reductions, dose delays and early stoppage for chemotherapy and the total combined number of moderate and severe chemotherapy-associated toxicities between intervention group and waitlist controls.

2.2 Secondary Objectives:

2.2.1 Examine specific inflammatory markers (CRP, IL-6, TNF- α receptor II [TNF-RII]) in relation to baseline MM and FM and examine differences in changes in inflammatory markers between intervention group and waitlist controls.

2.2.2 Examine the impact of intervention versus control and RT-induced body composition changes on the pharmacokinetics [PK] of 5-FU and oxaliplatin between baseline and 4 months of RT.

2.3 d3 Creatine Objectives:

2.3.1 Test whether resistance training during chemotherapy (FORCE intervention group v. control) increases d3 creatine muscle mass at 6 months.

2.3.2 Evaluate the association of d3 creatine muscle mass with changes in functional status and strength during chemotherapy.

2.3.3 Evaluate the association of d3 creatine muscle mass with chemotherapy toxicity and relative dose intensity.

2.3.4 Evaluate the association of d3 creatine muscle mass with cancer-related biomarkers, including inflammation, CEA levels and cardiometabolic risk factors.

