Participants randomized to the usual care (U) group will be instructed to refer to their physician regarding what forms of exercise are safe for them, given their specific medical history. The U group will be told to continue whatever exercise program they have been undertaking up to enrolling in the study, but not to increase exercise or begin weight-lifting over the period of study participation (See Appendix 13.9). Participants will be sent a contact card halfway through the intervention reminding them of the follow-up visit. At the conclusion of participation, they will be offered: Emailed link to WebExercise routine; a set of resistance bands; a 30-minute interview with FORCE exercise professional; and a sample of protein powder.

3.11 Pharmacokinetics study:

Up to 30 individuals, who are scheduled to receive 6 months of 5-FU, leucovorin and oxaliplatin (FOLFOX), will be given the option to participate in pharmacokinetic (PK) testing (see Section 4.14), in addition to the randomized intervention.

3.12 Compensation:

All participants participating at Kaiser Permanente, Penn State and Dana-Farber who are not participating in the PK study will receive a gift card either in person or by USPS as a thank you for completing the baseline visit (\$25) and the follow-up visit (\$25). See Appendix 13.10 for example language to be included in thank card for those gift cards sent by mail. Patients participating in the PK study will receive a total of \$225 in gift cards by study completion- \$100 for each day that PKs are drawn and \$25 for the follow-up visit (total 3 cards). In addition, parking will be validated on the 2 days that PKs are drawn.

3.13 Photographs of study subjects:

Participants will be asked if they would be willing to have their photograph taken. If they are interested, they will be asked to complete the Media Consent form. For those who consent, photographs of study participants will be taken during clinic visits (completing questionnaires, physical assessment testing, talking with study staff), to use in research presentations, for conferences and workshops, where the Investigator(s) present the study. Dana Farber Cancer Institute is excluded from this as they will not ask their participants if they are willing to be photographed.

3.14 Sharing of results with subjects:

All participants will be provided with whole body DXA results, both Baseline and Post-Intervention, after the conclusion of participation (See Appendix 13.8.5).

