Assays for inflammation markers will be conducted in the laboratory of [name] at Boston Children's Hospital. High Sensitivity C-Reactive Protein (hsCRP): The concentration of CRP will be determined using an immunoturbidimetric assay on the Roche P Modular system (Roche Diagnostics - Indianapolis, IN), using reagents and calibrators from Roche. Interleukin-6 (IL-6): IL-6 is measured by an ultra-sensitive ELISA assay from R & D Systems, Minneapolis, MN. The assay employs the quantitative sandwich enzyme immunoassay technique. TNF α -receptor II: TNF-RII is measured by an ELISA assay from R & D Systems. The assay employs the quantitative sandwich enzyme immunoassay technique.

4.14 Pharmacokinetic (PK) measurements:

5-FU and oxaliplatin plasma PK will be determined during the first cycle of FOLFOX following study enrollment and during the FOLFOX cycle at approximately 4 months post enrollment. Blood samples (5 mL, EDTA treated tubes) will be obtained from each patient at the following seven time points on each study day: prior to OX infusion; at the end of OX infusion (before 5-FU); after 5-FU loading dose (but before 5-FU infusion); approximately 0.5, 1, 2 hours after the start of the 5-FU infusion; and at the end of the 5-FU infusion (approximately 46 hours). For samples obtained up to 4 hours after the start of 5-FU infusion, an intravenous saline lock catheter will be placed in the participant's forearm. A minimal waste sample (<2 mL) will be obtained prior to each study sample. Less than 60 mL (about ¼ cup) total of blood will be withdrawn during each of the two phases.

Samples will be immediately processed to plasma, labeled with the study ID and sample ID (i.e., PK1 and collection time) and stored at -80°C until analysis. Samples will be shipped on dry ice

to the Clinical Pharmacology Analytical Core (CPAC) at the Indiana University Melvin and Bren Simon Cancer Center (IUSCC). Each site will maintain a log of all collected specimens. When the site is ready to ship samples, they will submit that log (with anonymized study ID numbers and time point only) to the CPAC for verification that each participant had the required samples. See Appendix 13.8.6 for a summary of the KP PK blood draw protocol.

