9. STATISTICAL CONSIDERATIONS

9.1 Study design:

This randomized controlled trial of resistance training intervention in colon cancer patients receiving chemotherapy consists of two arms: an in-person and telephone-based intervention to promote home-based resistance training, and a wait-list, control group. After consent and baseline visit measurements, randomization assignment will utilize a covariate adaptive randomization procedure which ensures that equal numbers of patients are assigned to each study arm and that the two arms remain balanced on five key characteristics: site of participation [Kaiser Permanente vs Penn State vs Dana-Farber]; gender [male vs female]; cancer stage [stage II vs stage III], and duration of chemotherapy [3 months vs 6 months]; planned chemotherapy regimen [FOLFOX vs CAPOX vs capecitabine vs 5-FU/LV]. This randomization method (also known as the minimization method) has been demonstrated to outperform simple randomization or stratified randomization in terms of achieving balanced groups, particularly in smaller trials with multiple important prognostic factors.

The primary objective of this trial is to compare the effect of a RT intervention versus a wait-list control on chemotherapy dose reductions, dose delays, early discontinuation of chemotherapy and treatment-related toxicity. The secondary objective is to compare the effect of the intervention versus wait-list control on changes in inflammatory biomarkers, and the tertiary objective is to compare pre and post intervention pharmacokinetics of 5-FU and oxaliplatin. The d3 Creatine objective is to compare the effect of a RT intervention versus a wait-list control on d3 creatine muscle mass at 6 months.

9.2 Sample size, accrual time and study duration:

One hundred and eighty (180) participants will be recruited and randomized over a total of 3.5 years. Patient involvement and data collection will last approximately 6 months.

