Pharmacokinetics: As 5-FU is known to undergo nonlinear disposition, compartmental modeling will be conducted using nonlinear mixed effects analysis with NONMEM (Icon Development Solutions, Hanover MD). NONMEM allows for simultaneous estimation of fixed-effects values (e.g. CL and V) and random-effects values (e.g. inter-individual, inter-occasional, and residual unexplained variability). Previous models of 5-FU and oxaliplatin²⁸ have been reported and will serve as a basis for development of the structural model. The final structural (e.g. 1- vs. 2-compartment) and error models (e.g. additive or proportional) will be chosen based on minimization of the objective function value (OFV, $-2 \log$ likelihood) and evaluation of diagnostic plots generated in R. During the covariate selection process, various measures of body composition (e.g. MM, MM/FM ratio) will be compared to identify the contribution of these parameters to PK variability in colon cancer patients. Pre- and post-intervention PK parameters (e.g. CL, V) will be compared using a paired t-test.

9.3.3 d3 creatine endpoints:

We will first assess the distribution of the baseline covariates by FORCE randomization arm. Most outcomes will be treated as continuous variables and we will fit linear regression models (e.g., for the continuous outcomes such as change in d3 creatine muscle mass, SPPB and SF-36 score, grip strength, relative dose intensity, and values of inflammatory markers, CEA and cardiometabolic risk factors). We will assess departures from regression model assumptions primarily by diagnostic plots of residuals, with attention to detection of non-constant variance of errors and detection of outliers that may indicate the need for a variance stabilizing transformation of the dependent variable. In secondary analyses, when considering outcomes dichotomously, we will fit logistic regression models (e.g., for abnormal CEA values).

Aim 1 is a randomized comparison of the FORCE resistance training intervention to the waitlist control. Analyses in Aims 2-4, however, are subject to confounding. Our *a priori*

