set of potential confounders for cross-sectional analyses at baseline includes age, sex, body mass index or weight, race/ethnicity and tumor stage. For longitudinal analyses, potential confounders also include chemotherapy type, intervention assignment and time from surgery and/or chemotherapy start to assessment. We will include those covariates resulting in a 10% or more change in the d3 creatine muscle mass regression coefficient. The change-in-estimate approach to confounder selection performs well with regard to power, bias, mean squared error and confidence interval coverage.

9.3.4 Power:

Given previous exercise studies in cancer patients, we assume approximately 10% drop out with no follow-up DXA and blood draw for biomarker assessment. We expect chemotoxicity metrics (RDI, # toxicities) to be assessed on the full sample. We have sufficient power (.80) to detect a between arm difference in means of at least .42 standard deviation (s.d.) units (two-sided t-test, $\alpha=.05$) in Aim 1 analyses of chemotoxicity. With an expected RDI s.d. of 17.3⁴⁵, the minimum detectable difference in mean RDI is 7.3%, which is clinically meaningful and similar to effects found with a study of exercise among breast cancer patients receiving adjuvant chemotherapy⁴⁵. With the expected loss to follow-up and reduced sample size of 81 per group, the minimum detectable between arm difference in mean change is .44 units, which is considered in the “small” to “medium” range in effect size using the terminology and classification of Cohen. Relevant to Aim 4, on pharmacokinetics, a sample size of 30 subjects will provide sufficient power (.80) to detect a mean change of at least 0.5 s.d. units (two-sided t-test, $\alpha=.05$). Given previous data²⁶, the minimum detectable change in clearance of oxaliplatin or 5-FU due to RT is 15%.

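### The PK sub-study credits its detectable clearance change to resistance training, but its only named test is a before/after paired t-test that does not compare the arms

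*Protocol*

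**What the plan says.** **Objective.** The protocol states the PK objective in three ways.

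- Section 2.2.2, as a secondary objective: "Examine the impact of intervention versus control and RT-induced body composition changes on the pharmacokinetics".
- Protocol Summary, Secondary Objective b, which drops the control comparison: "To examine the impact of RT induced body composition changes on the pharmacokinetics (PK) of 5-FU and oxaliplatin".
- Section 9.1, with a lower rank and only a before/after contrast: "the tertiary objective is to compare pre and post intervention pharmacokinetics of 5-FU and oxaliplatin".

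**Cohort and timing.** Under section 3.11, up to 30 people scheduled for six months of FOLFOX "will be given the option to participate in pharmacokinetic (PK) testing (see Section 4.14), in addition to the randomized intervention". Nothing limits this to one arm. Section 4.14 places the draws "during the first cycle of FOLFOX following study enrollment and during the FOLFOX cycle at approximately 4 months post enrollment".

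**Analysis.** Section 9.3.2 describes a NONMEM model whose named candidate covariates are body-composition measures. It then adds one test: "Pre- and post-intervention PK parameters (e.g. CL, V) will be compared using a paired t-test". It does not say whether that test pools the arms or uses the RT arm alone.

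**Power.** Section 9.3.4 says that "a sample size of 30 subjects will provide sufficient power (.80) to detect a mean change of at least 0.5 s.d. units", and then that "the minimum detectable change in clearance of oxaliplatin or 5-FU due to RT is 15" per cent.

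The SAP text available covers the primary endpoints only and has no PK analysis.

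**The concern.** A change measured in the same people over four months of chemotherapy can have many causes: time, cumulative drug exposure, recovery from surgery, or RT. Only the randomised comparison separates RT from the rest. The sub-study can include controls, yet the named test does not use them as a comparator.

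Two errors can follow. If clearance drifts equally in both arms, a significant paired test could be reported as an RT effect. If only the RT arm changes, pooling dilutes the effect. The 30-subject power statement also suggests a sensitivity to RT effects that the sub-study does not have. The primary dose-intensity and toxicity analyses are not affected.

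**Working it through.** **Inputs from the documents.** n = 30, mean change 0.5 SD, power 0.80, two-sided alpha 0.05 (9.3.4); at most 30 volunteers from the randomised participants (3.11); paired t-test (9.3.2).

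**Inputs not given, so assumed.** The arm split is taken as 15 v 15, with 20 v 10 as a check; PK participation is not one of the balancing factors in 9.1. The correlation between the two draws is taken as 0.3, 0.5 and 0.7. The SD of the change in clearance is not stated, so results are in SD-of-change units. Dividing 15% by 0.5 implies an SD of 30%, but that is back-calculated. The reference cited for the 15% is listed as an exercise feasibility study in recurrent ovarian cancer, so the SD cannot be traced within the document.

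**Step 1. Reproduce the plan's figure as a paired test on 30 changes.**

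- Normal approximation: power = Φ(0.5 × √30 − 1.96) = Φ(0.779) = 0.78. Detectable change = (1.960 + 0.842)/√30 = 0.51 SD.
- Exact noncentral t, 29 df: power 0.754; detectable change 0.529 SD; 34 pairs are needed for 0.80 at 0.5 SD.

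The stated 0.5 SD is thus, to rounding, the figure for an overall change in all 30 people. The gap between 0.75 and 0.80 is minor.

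**Step 2. What a paired test estimates.** Let c be the mean change common to both arms, δ the RT effect, and f the fraction of the cohort in the RT arm.

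- Pooled test: c + fδ.
- RT arm only: c + δ.

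Neither equals δ unless c = 0, and the pooled version also needs f = 1. Two cases show the size:

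- δ = 0 and c = 0.5 SD: the pooled test is significant with probability 0.75, although RT did nothing.
- c = 0, δ = 0.5 SD, f = 0.5: the pooled mean is 0.25 SD and power is about 0.26.

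**Step 3. The comparison that 2.2.2 asks for.** For unadjusted change scores the noncentrality is d/√(1/n₁ + 1/n₂), with 28 df.

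- 15 v 15: √(2/15) = 0.365 and noncentrality at 0.5 SD is 1.37, so power is 0.26. The detectable difference is 1.06 SD, and the 95% CI half-width is 2.048 × 0.365 = 0.75 SD.
- 20 v 10: √(1/20 + 1/10) = 0.387; power 0.24; detectable difference 1.12 SD.
- Detecting 0.5 SD between arms with power 0.80 would take 64 per arm.

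**Step 4. ANCOVA on the baseline value.** This was simulated with equal variance at both draws and chance baseline imbalance included. Units are SDs of change.

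| Assumed correlation | Power at 0.5 SD, 15 v 15 | Detectable difference, 15 v 15 | Detectable difference, 20 v 10 |
|---|---|---|---|
| 0.3 | 0.36 | 0.87 | 0.92 |
| 0.5 | 0.32 | 0.94 | 0.99 |
| 0.7 | 0.29 | 1.00 | 1.06 |

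**Step 5. RT arm alone, 15 pairs.** Power at 0.5 SD is 0.44 and the detectable change is 0.78 SD, with no control.

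**Step 6. Does other text supply the arm contrast?** The intent-to-treat sentence in 9.3.1 does not specify a PK contrast. Intervention assignment appears as a potential confounder in 9.3.3, but for the d3-creatine models. The NONMEM covariate step can serve the body-composition half of 2.2.2; no arm term is named for the other half.

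**The case against.** The best reply is that 2.2.2 is the outlier. The abstract, the summary objective and 9.1 describe the PK work as body composition or before versus after, and the NONMEM covariate model matches the body-composition purpose. On that reading the lighter repair is to drop the control comparison from 2.2.2 and the attribution to RT from 9.3.4, rather than add a contrast with power of about 0.3. This stands as a coherent alternative. It still concedes that the 9.3.4 claim is unsupported, and it would leave unused the only comparison in the cohort that isolates RT.

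Three further points have weight.

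- The split is unknown and a mostly-RT cohort is not excluded, so the 15 v 15 figures and the RT-only power of 0.44 are illustrations. An RT-only test gains power with more RT pairs but remains uncontrolled.
- The log scale, ANCOVA and the correlations proposed here are choices from outside the documents.
- The SAP reports randomisation as complete (183 participants), so revised prospective power matters less than fixing the contrast before the PK data are analysed.

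The rank of the objective and the label of the second draw are editorial. Parts of the SAP were not available, so the absence of a PK arm comparison is a statement about the text supplied.

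**Conclusion.** The concern holds and should be fixed. The test named in 9.3.2 cannot support the attribution to RT in 9.3.4, and the intervention-versus-control part of 2.2.2 has no specified analysis in the text supplied. That conclusion does not depend on the arm split.

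The size does. Assuming 15 v 15, the detectable RT effect is 1.06 SD of change unadjusted, or 0.87 to 1.00 SD with baseline adjustment at the assumed correlations. That is 1.7 to 2.1 times the stated 0.5 SD. The calculations take all 30 places as filled with both draws complete; with 27 completers (14 v 13) the unadjusted figure is 1.12 SD. The consequence is confined to an optional sub-study.

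**What to change.** 1. **Section 9.3.2, or a PK analysis plan finalised before the PK data are analysed.** Replace the paired-test sentence with: *The RT effect on PK will be estimated by ANCOVA of 4-month log CL and log V on the baseline value and randomised arm, and reported with a 95% CI. The overall baseline-to-4-month change is descriptive.* An arm-by-occasion term in the NONMEM model is an acceptable alternative, but one of the two should be named as primary. Keep the body-composition covariate analysis.
2. **Section 9.3.4.** Delete the attribution to RT. State that 30 pairs give power 0.75 at 0.50 SD (0.80 at 0.53 SD) for an overall change only. Add that, if the arms split 15 v 15, the detectable difference between arms is about 1 SD of change, with the split and correlations marked as assumptions. Keep the 15% only as an overall change, with its SD and source.
3. **Objective.** Use one wording and one rank in the Protocol Summary, 2.2.2 and 9.1. If the control comparison is dropped from 2.2.2, item 1 is no longer required by the objective, but the attribution to RT must still go.
4. **Label.** Call the second draw the 4-month draw, since the intervention runs for about six months (section 3.8).

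**Cost.** Wording only: no extra patients, samples or visits. The stated sensitivity becomes less favourable, and the RT-versus-control PK result has to be presented as an imprecise estimate.

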11. DATA PRIVACY AND SECURITY

Disclosure of PHI to non-KPNC workforce

PHI will be disclosed to members of the Data Safety and Monitoring Board (DSMB) as well as an independent contractor, [name]. The DSMB members will oversee and monitor the study to ensure participant safety and the validity and integrity of the data. [name] will act as exercise intervention liaison, including overseeing exercise sessions, case review with trainer, and contact with DSMB. Types of PHI that will be disclosed include dates.

Disclosure of deidentified datasets to non-KPNC workforce

The following investigators and research staff from collaborating institutions will receive deidentified datasets (i.e., contains no PHI identifiers):

- [name], MPH, Dana Farber Cancer Institute
- [name], MPH, FACSM, FTOS, The Pennsylvania State University, Hershey Medical Center
- [name], [name], University of British Columbia
- [name], Pennington Biomedical Research Center, Louisiana State University
- [name], Pharm. D., Indiana University
- [name], independent contractor, Kensington, CA

Deidentified datasets will include intervention data such as exercise adherence; study measure and questionnaire data from baseline and follow-up data collection; chemotherapy data and demographic data.

Data transfer

All data will be shared securely with investigators and staff via KPNC secure file transfer.

Data storage

All study data including data with PHI will be stored electronically on a secure, password protected KP server behind a firewall and in an online, secure, password protected REDCap database. Only approved research study staff have REDCap access. REDCap data will be archived off the server within 12 months after data collection ends. No PHI data will be stored for any part of the study on an endpoint computing device or removeable media (i.e., workstation, laptop, flash drive, CD).

Blood biospecimen samples will be stored at Kaiser Permanente Northern California and Dana Farber Cancer Institute. Samples will be kept until they are used up for future studies or the Principal Investigators decide to destroy them.

